14.2. Analysis Populations

Safety analyses will be performed on a Safety Set, defined as all patients who received at least 1 infusion of ORGN001.

Efficacy analyses will be performed on the Full Analysis Set (FAS), defined as patients with a confirmed diagnosis of MoCD Type A who have no antenatal and/or postnatal brain imaging prior to initiation of treatment with ORGN001 that indicates cortical or subcortical cystic encephalomalacia or clinically significant intracranial hemorrhage.

Additionally, two modified Full Analysis Sets (mFAS) will be used to support the analyses on the FAS:

- Neonate mFAS (NmFAS), [REDACTED]
- Pediatric mFAS (PmFAS) [REDACTED]

Available efficacy data of all patients excluded from the FAS will be displayed in listings and described in narratives.

14.3. Efficacy and Pharmacokinetic Endpoints

Primary Efficacy Endpoint:

- The primary efficacy analysis will be OS

Secondary Efficacy Endpoints:

[REDACTED]

- Changes in growth parameters (height, weight, BMI, head circumference) through Month 12
- Feeding pattern assessments through Month 12
- GMFCS-E&R results through Month 12
- Bayley-III Cognitive and Motor scaled scores and composite scores, as well as percentile ranks and age equivalents, through Month 12 (or WPPSI-IV scores, if applicable)
- The normative standard and scaled scores from the PEDI Functional Skills scales, including Self-Care, Mobility, and Social items through Month 12
- GMFM-88 results through Month 12

14.4. Demographics and Baseline Characteristics

All demographic and Baseline characteristics information will be summarized for the Safety Set, the FAS, the NmFAS, and the PmFAS.

14.5. Patient Disposition and Extent of Exposure

The number of patients screened, treated, continuing treatment after confirmation of enrollment criteria, and completing the 12-month and 36-month study periods will be tabulated. Reasons for any patient withdrawals will be provided. The number of patients in the safety and efficacy analysis sets, along with reasons for exclusion from analysis sets, will be tabulated.

Extent of exposure with ORGN001 will be summarized among both the Safety Set and FAS, with respect to number of infusions, number of missed and partial infusions, and duration of treatment period.

14.6. Prior and Concomitant Medications

Prior and concomitant medications will be summarized using the Safety Set. Listings of prior and concomitant medications will be produced, as will listings of anticonvulsants.

[figure not shown]
Medications will be coded using the World Health Organization Drug Dictionary (WHODrug) version 01 Sep 2013 or higher. Medication summaries will be presented by WHODrug Anatomical Therapeutic Chemical (ATC) and by WHODrug generic name.

14.7. Efficacy Analyses

Efficacy analyses will be performed on the FAS, NmFAS, and PmFAS. Baseline is defined as the last available assessment prior to treatment with ORGN001.

14.7.1. Use of Natural History Study ALX-MCD-502

Data from natural history study ALX-MCD-502 will be used to support the current study in order to guide interpretation by representing the expected clinical time course for patients with MoCD Type A in the absence of ORGN001 treatment.

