14.7.3 Secondary Efficacy Analyses	

Section	Description of Change
	
Text added:
 
 “Body weight, length, head circumference, and BMI will be analyzed by converting each parameter to age-adjusted z-scores and age percentiles, and descriptive statistics will be presented to each parameter through Month 12.” “Changes in motor function through Month 12 will be summarized based on data from the administration of the GMFCS-E&R, which is a 5-level classification system that classifies gross motor functional capabilities and limitations as usual performance in the home, school, and community setting.” “The Bayley-III Cognitive and Motor scaled scores and composite scores, as well as percentile ranks, and age equivalents will be summarized through Month 12. Where appropriate, the WPPSI-IV will be used instead of the Bayley-III.” “PEDI standard and scaled scores will be summarized by self-care, mobility, and social function domains through Month 12.”
Appendix B Blood Sampling Volume Tables	
 PK sampling time point blood draws added 1-2 hours after the EOI Total amount of blood drawn per time point adjusted [REDACTED]; total amount of blood drawn per 12-month study period adjusted [REDACTED].

Table 5: Summary of Changes Between Amendment 2 and Amendment 3

Section	Description of Change
Cover page	
 Protocol title updated to reflect addition of infants and children to the study population. (This change has been carried through to all other locations in which the protocol title is shown.) Updated responsible study personnel.
Sponsor Signature Page	
 Updated responsible medical officer. Added additional signatories.
Procedures in Case of Emergency	Updated contact information for reporting SAEs.
2 Synopsis	
 The study period has been adjusted to accommodate long-term follow-up until approval or decision reached on further development of ORGN001, and last patient completion date has been adjusted to 4Q2022. The study background/ rationale, study objectives, endpoints, methodology, inclusion/exclusion criteria, and statistical methods have been updated to reflect the changes detailed in sections below that have been made to expand the study subject population to include older infants and children with MoCD.

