2.1. Background

Molybdenum cofactor deficiency (MoCD) is a rare, life-threatening, autosomal recessive, inborn error of metabolism that is characterized by disruption of the metabolic pathway for production of molybdenum cofactor (MoCo). Molybdenum cofactor is essential for functioning of the enzymes sulphite oxidase (SO), xanthine oxidoreductase, and aldehyde oxidase activity (Schwarz 2009). The loss of SO activity is responsible for the severe and rapidly progressive neurologic damage seen in neonates presenting with MoCD (Reiss 2003; Schwarz 2009). Less frequently, older infants and children may present with neurologic symptoms related to MoCD such as seizures, movement disorder, and developmental delay/disability that appears to have a less rapidly evolving course.

Although there are three types of MoCD, two-thirds of MoCD patients have Type A, which is due to a mutation in the *MOCS1* gene localized on chromosome 6p21.2. In MoCD Type A, the first of four synthetic steps in the formation of molybdenum cofactor is interrupted, and guanosine triphosphate (GTP) cannot be converted into cyclic pyranopterin monophosphate (cPMP). Diagnosis of MoCD Type A in neonates is based on clinical and laboratory presentation (eg, seizures, exaggerated startle response, high-pitched cry, intracranial hemorrhage, axial hypotonia, limb hypertonia, feeding difficulties, elevated urinary sulfite and/or S-sulfocysteine [SSC], or low or absent uric acid in the urine or blood) and is then confirmed by genetic testing. The clinical presentation after the neonatal period appears to be more heterogeneous and may progress less rapidly.

The biosynthetic pathway for MoCo synthesis involves 3 major steps; see [Figure 1](#) (Schwarz 2009).

Figure 1: The Metabolic Pathway for Molybdenum Cofactor

The incidence of MoCD is estimated to be between 1/100,000 and 1/200,000 newborn babies worldwide (Schwahn 2015). Affected individuals with MoCD Type A usually present as

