2.4. Rationale for Patient Population

Preliminary data suggest that the metabolic derangement of MoCD starts in utero and patients demonstrate symptoms associated with sulfite toxicity within hours of birth ([Veldman 2010a](#); [Hitzert 2012a](#)). This observation supports the premise that irreversible neurologic injury may occur very early in life and that immediate postnatal treatment with ORGN001 may alter the outcome of this devastating disorder.

Selection of the patient population to determine ORGN001 efficacy and safety in Study ALXN1101-MCD-202 was based on the population that is most likely to benefit from ORGN001 treatment. Considerations were given to the age of onset of the disease and the extent of CNS injury at time of diagnosis and/or planned treatment. Consequently, the population initially identified to be enrolled in Study ALXN1101-MCD-202 comprised patients from 1 to 28 days of age (inclusive) at the time of first ORGN001 dose administration (neonates), with Day 1 of age corresponding to the day of birth. However, the clinical presentation after the neonatal period appears to be more heterogeneous and may progress less rapidly in some patients. In an effort to more fully characterize the potential impact of ORGN001 in MoCD Type A, the study has thus been modified to include infants and children with MoCD Type A, who are treatment-naïve or may have previously received ORGN001 through the early access program (EAP). Infants are defined as those from 29 days to <2 years of age. Children are defined as those from 2 to 5 years of age (inclusive). In neonates, eligibility will be determined by prenatal genetic diagnosis of MoCD Type A or presence of signs and symptoms consistent with the diagnosis of MoCD Type A. Genetic testing will be performed to confirm the MoCD Type A

genotype. In infants or children, eligibility will be determined by confirmed genetic diagnosis (genetic confirmation of the diagnosis of MoCD Type A may be obtained after initiation of ORGN001 therapy in certain cases), biochemical profile, and clinical presentation consistent with MoCD Type A.

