4.3.1. Demographic Data

At Screening/Baseline, the patient's date of birth, gender, gestational age, race, and ethnicity will be recorded. The date of first recognition of MoCD-associated signs or symptoms will be documented, as available.

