14.7.2. Primary Efficacy Analysis

The primary efficacy analysis will summarize OS, defined as the interval in months from the date of birth to the date of death or date last known alive (patients still on study will be censored at the data cutoff date), whichever occurs first.

The analysis of OS will be based on the Kaplan-Meier methodology for estimation of survival parameters. The median duration of OS will be estimated based on the 50th percentile of the Kaplan-Meier distribution; additional summary statistics, including the 25th and 75th percentiles, 95% confidence intervals (CIs) on the median and the other percentiles and proportion of censored patients. The analysis of OS will be done using the FAS, the NmFAS, and the PmFAS.

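### Section 14.7.1 states no alignment by onset between the natural-history reference and a full analysis set that now includes later-presenting patients, so pooled survival could exceed the reference with no drug effect

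*Combined protocol and SAP*

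**What the plan says.** Section 2.6 explains why the trial has neither a placebo arm nor an active control. Section 14.7.1 supplies the outside reference in a single sentence: ALX-MCD-502 is to support the study and help interpret it by "representing the expected clinical time course for patients with MoCD Type A in the absence of ORGN001 treatment". The visible text gives no split, matching or weighting, and no test, hazard ratio or margin against that study.

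Section 2.4 says that the study began with neonates (first dose at 1 to 28 days of age) and that "the study has thus been modified to include infants and children with MoCD Type A, who are treatment-naïve or may have previously received ORGN001". Infants run from 29 days to under 2 years, and children from 2 to 5 years. The same section says that "the clinical presentation after the neonatal period appears to be more heterogeneous and may progress less rapidly in some patients", and Section 2.1 that "Less frequently, older infants and children may present with neurologic symptoms related to MoCD".

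Under Section 14.2 the FAS is the main efficacy set. It requires a confirmed Type A diagnosis and the absence of certain brain lesions before treatment, and it has no limit on age or onset. NmFAS and PmFAS support it; their definitions are blacked out. Section 14.7.2 counts overall survival (OS) from birth, by Kaplan-Meier: "The analysis of OS will be done using the FAS, the NmFAS, and the PmFAS". Section 14.1 sets no sample size and ties success to the OS rate without a threshold. On onset, Section 4.3.1 says: "The date of first recognition of MoCD-associated signs or symptoms will be documented, as available".

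**The concern.** A one-arm survival curve shows benefit only when it is set against what would have happened without treatment, and ALX-MCD-502 is the only untreated reference that the visible analysis plan names. If untreated risk differs between neonatal-onset and later-onset disease, the height of a pooled curve depends on the mix of the two. With no enrolment quota, nothing ties the mix in the FAS to the mix in ALX-MCD-502. A difference in survival could then come from who was enrolled and not from the drug.

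The protocol's age groups do not settle this. They rest on age at dosing or consent (Sections 4.1 and 7.2), so a patient with neonatal onset who first enters at age 2 is counted as a child alongside true late-onset cases. Because OS starts at birth, such a patient is also credited with two years of survival that were a condition of entry. This second bias is separate from the onset mix and needs its own remedy.

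**Working it through.** The documents give no onset shares, no survival by onset, and no sample size or success threshold. There is no planned figure to reproduce, and the size of the bias cannot be calculated from the documents alone. What follows shows its direction and a range under stated assumptions, with no drug effect throughout.

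**Inputs**

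- Untreated neonatal-onset median of 36 months: Section 2.3 gives 3 years for MoCD of all types; used here as a proxy.
- Exponential survival: assumption.
- Late-onset hazard equal to *k* times the neonatal-onset hazard, *k* = 0.25 to 0.5: assumption.
- Late-onset share *p* = 10% in ALX-MCD-502: assumption.
- Late-onset share *q* in the FAS: varied.

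**Step 1: onset mix alone.** At 36 months, S_neo = 0.50 and S_late = 0.5^k, which is 0.707 for k = 0.5 and 0.841 for k = 0.25. Each pooled curve is a weighted average, so

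FAS minus reference = (q − p) × (S_late − S_neo).

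| FAS late-onset share q | k = 0.5 | k = 0.25 |
|---|---|---|
| 10% | 0 | 0 |
| 20% | 0.10 × 0.207 = +2.1 points | 0.10 × 0.341 = +3.4 points |
| 30% | 0.20 × 0.207 = +4.1 points | 0.20 × 0.341 = +6.8 points |
| 50% | 0.40 × 0.207 = +8.3 points | 0.40 × 0.341 = +13.6 points |

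With the shares exchanged (p = 30%, q = 10%) the result is −4.1 and −6.8 points. If k = 1 it is zero whatever the shares.

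**Step 2: sensitivity to the 36-month proxy.** Take p = 10%, q = 50% and a late-onset median of 120 months, so S_late(36) = 0.5^(36/120) = 0.812.

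- Neonatal-onset median 36 months: 0.40 × (0.812 − 0.500) = +12.5 points.
- Neonatal-onset median 24 months: 0.40 × (0.812 − 0.354) = +18.3 points.
- Neonatal-onset median 12 months: 0.40 × (0.812 − 0.125) = +27.5 points.

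**Step 3: survival before entry.** Now drop any difference by onset and give every patient a 36-month median. Under the exponential, a patient who enters at age *a* months has a median OS from birth of a + 36: 60 months for entry at 24, and 96 for entry at 60. In a simulation of 400,000 patients, with later entrants spread evenly over ages 1 to 72 months, the median OS from birth was 44.5, 49.3 and 58.7 months when later entrants made up 20%, 30% and 50%. The true value is 36.

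**Step 4: does the remedy work?** Weighting the reference to the FAS mix removes the Step 1 gap by construction. At q = 30% and k = 0.5, both sides equal 0.7 × 0.500 + 0.3 × 0.707 = 0.562. Counting risk only from entry brings the Step 3 median back to 36.0 to 36.1 months, with a hazard ratio of 1.00, at every share tried. Neither step does the work of the other.

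**The case against.** The strongest reply is that the problem is read out of silence. Section 14.7.1 says neither that ALX-MCD-502 will be pooled nor that it will be split. A reader might infer that the plan compares the FAS with one undivided cohort, or that the comparator was left unchanged while the population grew. The text supports neither inference. The Summary of Changes lists Section 14.7.1 as wholly new relative to Amendment 2, so against that version the comparator text arrived with the widening.

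The plan also separates the treated patients in part. OS is reported in NmFAS and PmFAS as well as the FAS. If NmFAS holds patients dosed by day 28, it is already close to a neonatal-onset group, since anyone with signs by then has neonatal onset; only patients treated before signs are uncertain. The blacked-out definitions might even use onset. Further, ALX-MCD-502 has a supportive, descriptive role, the protocol hedges the slower course (it may apply, in some patients), and every share and hazard in the working is assumed. The 36-month figure may already include late-onset cases, and a constant hazard fits poorly with a disease in which neonatal death is common.

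All of this stands, and it makes the point conditional. It does not remove it. The FAS remains the main set, the reference is described for Type A as a whole, and no visible text pairs NmFAS or PmFAS with a matching ALX-MCD-502 subset. A descriptive contrast still shapes how the OS result is read.

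**Conclusion.** The point holds as a conditional one and should be settled before the comparison is made. As written, Section 14.7.1 would allow a biased reading of pooled FAS survival whenever the onset mixes differ. The bias favours ORGN001 if the FAS has the larger late-onset share and later-onset disease carries a lower untreated risk. It is zero if shares or risks are equal, and reverses if the FAS share is smaller.

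Under the Step 1 assumptions the spurious gain in 36-month survival is 2 to 3 points at a 20% FAS share, 4 to 7 at 30% and 8 to 14 at 50%. A shorter neonatal-onset median would make it larger. These figures illustrate; they do not estimate.

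A reader might go further and conclude that FAS survival will be inflated. The documents do not support that: they give neither late-onset share and no survival by onset, and the composition of ALX-MCD-502 is not described.

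**What to change.** In Section 14.7.1:

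1. Class trial and ALX-MCD-502 patients by age at first MoCD sign (28 days or younger, or older). The trial date is recorded under Section 4.3.1 only where available. Confirm first that ALX-MCD-502 recorded it; if not, state that limit.
2. Compare within onset group. For any pooled display, weight ALX-MCD-502 to the onset mix of the FAS. If NmFAS or PmFAS is set against natural history, name the matching subset.
3. Count time at risk only from age at first ORGN001 dose (delayed entry), because onset matching alone still credits survival before entry. Expanded-access patients were first dosed before enrolment and had to survive to it, so for them use age at enrolment.
4. Class patients treated before any signs with neonatal onset, and show a sensitivity analysis without them, since their untreated course is assumed.
5. State that no efficacy conclusion will be drawn from the unweighted pooled FAS contrast.

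The cost is some SAP text, one stratified display and a check of the ALX-MCD-502 data. The late-onset strata will be small with wide intervals, and the headline contrast may look less favourable.

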14.7.2. Primary Efficacy Analysis

The primary efficacy analysis will summarize OS, defined as the interval in months from the date of birth to the date of death or date last known alive (patients still on study will be censored at the data cutoff date), whichever occurs first.

The analysis of OS will be based on the Kaplan-Meier methodology for estimation of survival parameters. The median duration of OS will be estimated based on the 50th percentile of the Kaplan-Meier distribution; additional summary statistics, including the 25th and 75th percentiles, 95% confidence intervals (CIs) on the median and the other percentiles and proportion of censored patients. The analysis of OS will be done using the FAS, the NmFAS, and the PmFAS.

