4. INVESTIGATIONAL PLAN

4.1. Overall Study Design

This Phase 2/3, multicenter, multinational, open-label study is designed to evaluate the efficacy and safety of daily IV administration of ORGN001 to neonates, infants, and children with MoCD Type A. For the purposes of this study, neonate patients are defined as those from 1 to 28 days of age (inclusive) at the time of first ORGN001 administration, with day 1 of age corresponding to the day of birth. Infants are defined as those from 29 days to < 2 years. Children are defined as those from 2 years to 5 years (inclusive) at the time of informed consent.

Eligible neonates with a prenatal diagnosis of MoCD Type A will undergo Screening/Baseline assessments (eg, brain imaging) prior to or as soon as possible after birth and prior to receiving the first IV infusion of ORGN001. Given the life-threatening and devastating nature of the disease and the potential for a favorable benefit:risk profile for treatment with ORGN001, patients with a prenatal diagnosis may be treated prior to the onset of signs and symptoms associated with MoCD Type A. Additionally, if it is not possible to obtain brain imaging prior to treatment, the priority would be to treat the neonate and obtain brain imaging as soon as feasible afterwards. For those patients, the patient's legal guardians (per country-specific requirements) may be asked to provide informed consent for participation in the study prior to delivery. [REDACTED]

Eligible neonates who do not have a prenatal diagnosis of MoCD Type A but who have the onset of signs and symptoms that may serve as the basis for diagnosis will undergo Screening/Baseline assessments as soon as possible prior to receiving their first daily IV infusion of ORGN001. Data from procedures conducted as part of standard of care prior to study participation may be collected as part of Medical History. Genetic confirmation of the diagnosis of MoCD Type A may be obtained after initiation of ORGN001 therapy.

Eligible patients beyond the neonatal period with genetically confirmed evidence of MoCD Type A, a biochemical profile, and clinical picture consistent with MoCD Type may also be enrolled following completion of Screening/Baseline assessments. Data from procedures conducted as part of standard of care prior to study participation may be collected as part of Medical History. Genetic confirmation of the diagnosis of MoCD Type A may be obtained after initiation of ORGN001 therapy in certain cases.

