7.2. Patient Inclusion Criteria

Patients must meet all of the inclusion criteria to be considered eligible for enrollment in this study.

- Male or female neonatal patients (1 to 28 days of age [inclusive] at the time of ORGN001 administration, with day 1 of age corresponding to the day of birth), or infant (29 days to < 2 years of age) or child (2 to 5 years of age [inclusive]) with MoCD Type A, previously untreated with ORGN001 or treated with ORGN001 through the EAP
- In neonates, diagnosis of MoCD Type A, based on:
 - Prenatal genetic diagnosis, or
 - Onset of clinical and/or laboratory signs and symptoms consistent with MoCD Type A (eg, seizures, exaggerated startle response, high-pitched cry, axial hypotonia, limb hypertonia, feeding difficulties, elevated urinary sulfite and/or SSC, elevated xanthine in urine or blood, or low or absent uric acid in the urine or blood) within the first 28 days after birth
- In infants or children, diagnosis of MoCD Type A, based on:

- Confirmed genetic diagnosis (genetic confirmation of the diagnosis of MoCD Type A may be obtained after initiation of ORGN001 therapy in certain cases), biochemical profile, and clinical presentation consistent with MoCD Type A
- Parent or legal guardian must have signed the ICF prior to any study procedures being performed

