14.1. Determination of Sample Size

There will be no minimum or maximum number of patients for this study. The final sample size and determination of study success relative to efficacy will depend on the OS rate as each successive patient reaches study completion.

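### Overall survival is timed from birth by Kaplan-Meier in the FAS with no visible delayed entry, so patients who enrol after the neonatal period add guaranteed survival time and FAS survival is overstated whenever deaths occur

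*Combined protocol and SAP*

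**What the plan says.** Section 14.7.2 has OS "defined as the interval in months from the date of birth to the date of death or date last known alive" and estimates it by Kaplan-Meier. It adds: "The analysis of OS will be done using the FAS, the NmFAS, and the PmFAS". That section shows no redaction and gives no entry time, left truncation or landmark.

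Section 14.2 has the FAS "defined as patients with a confirmed diagnosis of MoCD Type A who have no antenatal and/or postnatal brain imaging" of the excluded kinds before treatment. No age limit is visible. The same section says that "two modified Full Analysis Sets (mFAS) will be used to support the analyses on the FAS"; the definitions of those two sets are redacted.

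Section 7.2 admits neonates, infants from 29 days to under 2 years, and children from 2 to 5 years inclusive, "previously untreated with ORGN001 or treated with ORGN001 through the EAP". In Section 4.1, "neonate patients are defined as those from 1 to 28 days of age (inclusive) at the time of first ORGN001 administration", so that label follows age at first dose and not age at joining this study.

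Section 14.1 states no sample size and says that "determination of study success relative to efficacy will depend on the OS rate as each successive patient reaches study completion". Section 14.7.1 uses natural history study ALX-MCD-502 to represent the untreated course, with no visible rule for aligning age at entry.

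**The concern.** A child who enrols at 40 months cannot have an observed death before 40 months. Kaplan-Meier from birth without an entry time still counts that child in every risk set from birth. Early denominators are too large, each early death among the neonates removes too small a fraction, and the curve sits too high even if the drug does nothing. Section 2.1 says death commonly occurs in the neonatal period, which later entrants are known to have survived.

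At stake is the estimate of the only primary efficacy endpoint. More patients do not reduce the error. An EAP patient first dosed as a neonate who joins later brings the same problem, because EAP deaths before joining never reach the FAS.

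**Working it through.** The plan states no sample size, event count or power, so there is no figure of its own to reproduce. The check measures the size of the error for a drug with no effect.

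**A small example.** Take five neonates, with deaths at 6 and 12 months, and five children who enter at 30 months. As planned, 12-month survival is (1 − 1/10)(1 − 1/9) = 0.80. With delayed entry it is (1 − 1/5)(1 − 1/4) = 0.60.

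**Inputs from the protocol.**
- Median survival 3 years (Section 2.3; for MoCD overall, not Type A alone and not the imaging-selected FAS).
- Follow-up 12 + 24 = 36 months from entry (Section 4.1).
- Entry ages from Sections 4.1 and 7.2. Five years inclusive is read as up to 72 months, with 60 months as the alternative.

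**Assumptions not in the documents.** Share p of later entrants (low shares first, since Section 2.1 calls later presentation less frequent), uniform entry ages, and hazard shape k.

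**Case A: later entrants have the same hazard as neonates.** S(t) = 2^(−(t/36)^k), so true 36-month survival is 50%. With at least 36 months of follow-up the planned curve tends to

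(1 − p)·E[S(36)/S(e)] over neonates + p·E[S(36)/S(e), or 1 if e > 36] over later entrants.

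For k = 1, where 36/ln 2 = 51.94:
- Neonates (0 to 28 days): 0.504.
- Infants (1 to 24 months): 0.5 × 51.94 × (2^(24/36) − 2^(1/36))/23 = 0.641.
- 1 to 72 months: [0.5 × 51.94 × (2 − 2^(1/36)) + 36]/71 = 0.866.

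So 20% infants gives 0.8 × 0.504 + 0.2 × 0.641 = 0.532, and 60% aged 1 to 72 months gives 0.4 × 0.504 + 0.6 × 0.866 = 0.721.

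| Planned 36-month survival (true 50%) | 10% later | 20% | 40% | 60% |
|---|---|---|---|---|
| Infants, k = 1 | 52% | 53% | 56% | 59% |
| 1–60 months, k = 1 | 54% | 57% | 64% | 70% |
| 1–72 months, k = 1 | 54% | 58% | 65% | 72% |
| Infants, k = 0.6 (falling hazard) | 54% | 56% | 60% | 64% |
| 1–72 months, k = 0.6 | 56% | 60% | 67% | 75% |

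Simulation agrees, and here delayed entry returns about 50%. Treatment-naive neonates alone give 50.4% (k = 1) or 52.5% (k = 0.6).

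**Case B: later entrants are milder**, as Sections 2.1 and 2.4 suggest. Neonates keep the 36-month median; later entrants have an exponential median m. The true value is 36-month survival among the births that the enrolled mix represents, each entrant at age e standing for 1/S(e) births.

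For 40% aged 1 to 72 months and m = 120, the birth weights are 0.6 × 1.009 = 0.605 for neonates and 0.4 × 1.243 = 0.497 for later entrants. Later entrants' 36-month survival is 2^(−36/120) = 0.812. The truth is (0.605 × 0.5 + 0.497 × 0.812)/1.102 = 64%. The planned curve gives 0.6 × 0.504 + 0.4 × 0.953 = 68%, about 4 points too high.

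| Overstatement by the planned curve, points | m = 36 | 72 | 120 | 240 |
|---|---|---|---|---|
| 20% infants | 3 | 2 | 1 | 1 |
| 40% aged 1–72 months | 15 | 7 | 4 | 2 |

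At m = 120 a pooled delayed-entry curve, by simulation, gives about 55% in both rows, against a truth of about 57% (20% infants) and 64% (40% aged 1–72 months). It is about 2 and 10 points too low.

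**The case against.** **The shared-hazard figures are too large for late-onset disease.** This stands. If later entrants carried little early risk, little of their pre-entry time was truly at risk. Case A is near an upper bound for genuinely late-onset patients. It fits better for neonatal-onset survivors who enter late, for example through the EAP, and their share is unknown.

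**Delayed entry is no clean cure.** This stands too. It recovers the truth only if entry age is unrelated to hazard. In a FAS of 10 with few later entrants its root-mean-square error is no better than the plan's: 0.164 against 0.161 for 20% infants at k = 1, and 0.177 against 0.167 at k = 0.6.

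**The plan already separates age groups through the NmFAS and PmFAS.** This stands in part. The synopsis and Section 14.7 list the three sets without putting the FAS first. But Section 14.2 makes the other two supportive, and their redacted definitions do not let a reader judge whether EAP patients first dosed as neonates fall in the NmFAS.

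**The analysis is descriptive.** True: no test, threshold or comparator is visible. A reader might infer from the success wording in Section 14.1 that the trial would reach a false efficacy conclusion. The documents do not support that, because no success rule is stated.

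A reader might also infer that the comparison with ALX-MCD-502 must favour the drug. That cannot be stated either: part of the error would cancel if those patients were aligned on entry age. And if no patient dies, both curves equal 1 and the survival estimate is not overstated.

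**Conclusion.** The concern holds. The stated rule counts pre-entry survival as time at risk, and the FAS curve from birth is too high whenever later entrants are present and deaths occur. Confidence is high in the mechanism and direction.

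Confidence in the size is moderate, because it rests on an entry-age mix and a later-entrant hazard that are not in the documents. The plausible range runs from about 1 point (few, milder infants) to 22 points (many later entrants sharing the neonates' 36-month exponential survival). The top of that range should not be read as the expected error. Treatment-naive neonates are almost unaffected.

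This should be fixed, as a biased primary estimate and not as a demonstrated wrong conclusion.

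**What to change.** Amend Section 14.7.2 as follows.

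1. Report OS from birth separately for neonates, infants and children by age at study entry. Group EAP patients by age at study Day 1, not at first EAP dose. Do not use the pooled FAS curve from birth as the lead estimate.
2. Within each group, put a patient in the risk set only from age at first study infusion. For infants and children, report survival conditional on reaching a stated age at which a pre-stated minimum number is at risk.
3. Show a pooled FAS delayed-entry curve only as a sensitivity analysis beside the planned curve. State that it is unbiased only if entry age is unrelated to hazard and may understate pooled survival if later entrants are milder.
4. Apply the same entry-age groups and entry rule to ALX-MCD-502 when it is shown alongside.

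**Cost.** A protocol and SAP amendment with ethics review (Section 17.1) and an entry-time option in the analysis program. Birth date is recorded (Section 4.3.1), and study infusions are documented. The first EAP dose date is not visibly required, since Section 8.2 covers only the 28 days before consent; grouping by Day 1 avoids needing it but discards EAP follow-up before joining.

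Expect smaller groups, wider intervals and less favourable figures. With 10 patients and 20 to 60% later entrants sharing the neonates' exponential hazard, the SD of pooled 36-month survival rises from 14–16 to 16–23 points. Under an illustrative minimum of four at risk, 10 infants always meet the rule. Ten entrants spread over 1 to 72 months fail to meet it before 36 months in 39% of simulated trials (1% with 20 entrants), and no estimate would then be given.
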